2.2 Secondary objectives

1. To compare the quantitative primary and secondary results of MagnetOsTM Granules to the results of Attrax® Putty from the AxA study (unpaired);
2. To investigate the relation between successful posterolateral fusion and interbody fusion, assessed at the one-year CT-scans used for the primary objective;
3. To compare the posterolateral spinal fusion rate of both MagnetOsTM Granules and autograft at one year with the fusion rates after two years, by using CT-scans;
4. To investigate the effect of blinding on perceived donor site pain, based on outcome measures reported by patients unblinded to the iliac crest donor site in comparison to these outcomes of the blinded patients from the AxA study;
5. To combine the study populations of the current study and the AxA study to investigate a) adjacent segment disease, in relation to length of construct and sagittal balance and b) risk factors for failures.

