2.3 Rationale for secondary objectives

Besides the primary research question on efficacy and safety, this study gives the opportunity to investigate very relevant scientific questions that can only be answered in human patients. Furthermore, combining the study data with the data obtained from the AxA study increases the power to study phenomena that occur less frequently.

1. Comparison of the quantitative results of MagnetOsTM Granules to Attrax® Putty

Since both the study designs are the same and have the same in- and exclusion criteria, it will be possible to compare the groups in a standard unpaired fashion. We did not power this comparison since it is a secondary aim, but the findings will be indicative with a considerable

sample size of 200 individuals (each with autograft at one side of their spine and MagnetOs™ Granules (n=100) or AttraX® Putty (n=100) at the other side).

2. Relation between posterolateral fusion and interbody fusion

Since this study will not exclude interbody fusions, and the effect of such interbody fusions on the posterolateral fusion masses is unknown, it is desired to determine the statistical relation between the posterolateral and interbody fusions.

3. Fusion rate after 2 years

There are indications that the percentage bony fusion continues to increase between 1 and 2 years.²⁶⁻²⁸ Whether this is graft related or a result of immobilization due to instrumentation is unclear. Nevertheless, it is important to determine the long-term fusion potential and behavior of MagnetOs™ Granules and autograft, and to compare these conditions. To limit the number of CT-scans at 2 years follow-up, only those patients that scored a doubtful fusion or non-union in any of the relevant levels at the one-year CT-scan will undergo an additional CT-scan.

4. Relevance of donor site pain

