7.1.2 Secondary study outcomes

1. Comparison of the quantitative primary and secondary results of MagnetOsTM Granules to the results of AttraX® Putty from the AxA study (unpaired);
2. Relation between successful posterolateral fusion and interbody fusion at one-year follow-up (assessed on CT-scans);
3. Posterolateral spinal fusion rate at two years follow-up compared to the fusion rate at one-year follow-up (assessed on CT-scans);
4. Effect of blinding on perceived donor site pain;
5. Incidence of long-term complications and relation with risk factors in the combined population of this study and the AxA study.

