 - EQ-5D-5L
 - ODI
 - NRS satisfaction
- VAS pain score
 - Back pain related to diagnosis
 - Leg pain related to diagnosis
 - Pain in left iliac crest
 - Pain in right iliac crest
 - Pain drawing
- Imaging
 - Standing anteroposterior and lateral radiographs
 - CT-scan of all patients with a doubtful fusion or non-union after 1 year, as assessed by the blinded observer
- Radiologic evaluation by treating surgeon (indications for failure or deformation / instability)
- Fusion assessment based on CT-scan by treating surgeon per level and per side in three planes, without the distinction between graft-related or non-graft-related fusion as described in Appendix C.

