7.8 Failures

Patients that need revision surgery that influences the fusion, will be considered failures and only excluded from the primary analysis and secondary outcomes related to the performance of MagnetOs™ Granules. This because the treatment effect on one side of the spine cannot be distinguished from the effect on the other side, so intention to treat analyses are not possible. Patients registered as failure will not be replaced, as the total number of patients takes this into account. Follow-up will continue according to the study protocol.

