9.1 Primary efficacy analysis

For the primary efficacy analysis, a comparison will be made between the fusion performance of the MagnetOsTM condition and the autograft condition, scored from the one-year (12-15 months) CT-scans according to the method described in Appendix C. Patients that required revision surgery influencing the fusion will be excluded from this analysis. In addition, if one side of a fusion-level is considered not evaluable, this level will be excluded. All evaluable scores will be dichotomized into fusion and no fusion. To allow inclusion of patients with fusion of multiple segments, without increasing the influence of these patients on the outcome, each side in these patients will be statistically considered as one condition. This means that the possible outcomes in these patients are: no fusion (if none of the levels is fused), equal fusion (if an equal number of segments is fused per side) or fusion at one side vs. no-fusion at the other side in case one side contains more fused segments than the other side.

The basis for the primary efficacy analysis will be the test of non-inferiority by performing a McNemar's test. The null hypothesis is that inferiority in fusion rate of the MagnetOsTM Granules compared to the autograft condition is greater than 15% (PAG-PMAG \geq 15%); the alternative hypothesis is that the MagnetOsTM Granules fusion rate will not be lower than the autograft success rate by more than 15% (PAG-PMAG< 15%).

In addition to the McNemar's test, a generalized estimating equations (GEE) model will be used to examine fusion on each side of a vertebra, while accounting for clustering of vertebrae within patients. The outcome will be fusion (yes/no) and the explanatory variable will be treatment. Analysis will result in an odds ratio for MagnetOsTM Granules vs. autograft and a 95% confidence interval.

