9.3 Analysis of secondary outcomes

1. To compare the quantitative primary and secondary results of MagnetOs™ Granules to Attrax® Putty a McNemar's test will be used as well as the mentioned GEE model;
2. As mentioned for the primary analysis, the odds-ratios and 95% confidence intervals for fusion rates of MagnetOs™ Granules and autograft will be calculated by using the GEE model. This model also allows to assess the effect of an additional interbody fusion;
3. For the comparison of the fusion rate after two years, the same method as for the primary efficacy analysis will be used;
4. VAS pain scores will be analyzed using the paired t-test, or Wilcoxon signed rank test in case of not-normally distributed data. To investigate the effect of blinding on perceived donor site pain, pain scores reported by the patients of this study and the AxA study will be compared using the unpaired t-test or Mann-Whitney U test.
5. To investigate risk factors of both study populations regression analysis will be done.

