The CT score will be dichotomized into fused and not fused. To allow the inclusion of patients with intended fusion of multiple segments, the sum of fusions on each side of the spine of these patients will be compared. If one side of a fusion-level is considered not evaluable, this will be excluded as well as the contralateral level. In multilevel patients, superiority (in number of fused levels) of one side, will be considered fusion and the other side non-fusion to prevent an unequal influence of patients with multi-level fusions. Although fusion assessment by this method gives more a "relative performance score" than a "fusion rate," analyzing the fusion rate of individual levels will not be adequate. There is strong reason to believe that the fusion rate will vary from patient to patient, so the fusion of individual vertebrae from one patient will not be independent. Since the study is randomized, this dependence should have no effect on a point estimate for the difference in fusion rates for MagnetOsTM Granules vs. autograft, but will certainly affect the standard error of the difference, thereby making standard statistical inference unreliable.

Although we know of no way of generating correct p-values or confidence intervals for differences in fusion rates using clustered data, it is possible to use a multi-level model (in which the clustering of vertebrae within patients is taken into account) to examine the effect of MagnetOsTM Granules and autograft on fusion, and using the vertebrae as the primary level of analysis. Such a model will produce an odds ratio instead of a difference in fusion rates. Since a sample size calculation based on a multi-level analysis requires a number of assumptions that cannot be supported by current data, we decided to perform sample size calculation based on the McNemar's test, and to use the multi-level model as a secondary analysis since it will make better use of the complete data while correctly taking the clustering into account.

Secondary Analysis

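### Section 9.3 item 3 does not say how the one- to two-year change in fusion per graft is estimated, or how patients without a two-year CT are counted

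*Combined protocol and SAP*

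**What the plan says.** Secondary objective 3 (section 2.2) is a comparison over time. It sets the rates of MagnetOs and "autograft at one year with the fusion rates after two years". Section 7.1.2 item 3 repeats it: "Posterolateral spinal fusion rate at two years follow-up compared to the fusion rate at one-year follow-up". Section 2.3 item 3 also wants the two grafts compared in the long term, and the aim in Appendix C is graft against graft after one and two years. The plan therefore wants two comparisons.

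The only analysis text is section 9.3 item 3: "For the comparison of the fusion rate after two years, the same method as for the primary efficacy analysis will be used".

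The method it points to (section 9.1, Appendix A) has two parts:
- A McNemar non-inferiority test of MagnetOs against autograft with a 15% margin. In multilevel patients, "superiority (in number of fused levels) of one side, will be considered fusion and the other side non-fusion".
- A GEE model: "The outcome will be fusion (yes/no) and the explanatory variable will be treatment". Section 9.3 item 2 and Appendix A also allow interbody fusion as a factor. Clustering is by side within level within patient.

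On who is scanned at two years, section 2.3 says: "To limit the number of CT-scans at 2 years follow-up, only those patients that scored a doubtful fusion or non-union". Section 7.3.3 lists a "CT-scan of all patients with a doubtful fusion or non-union after 1 year, as assessed by the blinded observer", and the footnote to Table 7.1 agrees. On revisions, section 7.8 says that such patients are "only excluded from the primary analysis and secondary outcomes related to the performance of" the product. Appendix C says only that two-year scans are read in the same way as one-year scans.

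**The concern.** A method built to compare two grafts at one visit has been assigned to an outcome that is partly a comparison of two visits. An analyst who follows item 3 literally gets a between-graft result at two years and no estimate of how much either graft gained. Section 9.4 does name a repeated-measurements analysis for changes in EQ-5D-5L, ODI and VAS, so the plan specifies a longitudinal method elsewhere but not here.

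The second gap is the denominator. The patients with a two-year CT are selected for not being fully fused. Whether the others are carried forward as fused, left out or treated as missing changes both the two-year rate and the between-graft difference. If this is not fixed in advance, the choice could be made after the two-year readings are known.

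**Working it through.** **The plan's own figure.** No number is given for the two-year comparison. The stated 84 for the primary test (80% power, one-sided alpha 0.05, margin 0.15, true difference 0, discordance 0.30) reproduces. The simple paired formula gives (1.645 + 0.842)² × 0.30 / 0.15² = 82.4, so 83. The exact power of the restricted-likelihood score test at 84 is 0.80098, the tabulated value. The sample size is not at issue.

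**Does the McNemar score register change?** Take a four-level patient and score each visit by the rule in Appendix A.

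| Fused levels, MagnetOs vs autograft | Score |
|---|---|
| Year 1: 2/4 vs 1/4 | MagnetOs fusion, autograft non-fusion |
| Year 2: 3/4 vs 2/4 | the same, although both sides gained a level |
| Year 2 instead: 3/4 vs 4/4 | MagnetOs non-fusion, although it gained a level |

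Appendix A itself concedes that the score measures relative performance more than a fusion rate. In single-level patients the score is absolute, and the problem does not arise.

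**Does the GEE register change?** Its outcome, fusion of each side at each level, is absolute and so suitable. Its terms are treatment and, optionally, interbody fusion. There is no visit term and no treatment-by-visit term.

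**Denominator, single level.** Inputs from section 4.4: 50% fusion per side and 70% concordance, so 30% discordance. I assume that these hold in single-level patients and that a scan is due unless both sides are read as fused.
- Both sides fused, not rescanned: 0.50 − 0.30/2 = 0.35.
- Rescanned: 1 − 0.35 = 0.65.
- One-year rate per side among the rescanned: (0.50 − 0.35)/0.65 = 0.231, against 0.50 overall.
- If those not rescanned count as fused on both sides, they add nothing to a between-graft difference. Leaving them out multiplies it by 1/0.65 = 1.54, so a 5-point deficit reads as 7.7.
- With 60% concordance the rescanned rate is 0.20/0.70 = 0.286 and the factor 1.43. With 80% they are 0.10/0.60 = 0.167 and 1.67.

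Suppose a share c of non-fused sides fuse during year two and none is lost (c is assumed; the documents give none). The two-year rate is 0.50 + 0.50c with carry-forward and (0.15 + 0.50c)/0.65 in the rescanned only. At c = 0.30 these are 65% and 46%. For any c below 0.35 the rescanned-only rate lies under the one-year 50%, although no side lost fusion.

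**What carry-forward costs.** Only patients read as not fully fused get a second reading, so false negatives can be corrected while false positives in fully fused readings stand. Assume a reading error e, independent at each reading, and no true change. The false rise per side is the chance that a side is read fused and would be read non-fused on repeat, e(1 − e), times the chance that the other side is read fused at one year, 0.50. For e = 5%, 10% and 15% this gives 2.375, 4.5 and 6.375 points.

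**Multilevel patients, illustration only.** The section 4.4 inputs describe the two sides of a whole fusion trajectory. Applying them to each level under a latent-normal model (left-right correlation sin(0.2π) = 0.588, either wholly between patients or split 70/30 between patient and level) gives, by simulation, 13–18% not rescanned and a factor of 1.15–1.21 for three levels, and 6–11% and 1.06–1.12 for six. The documents give neither the mix of levels nor the correlation between them.

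**The case against.** McNemar's test is a paired binary test, so the words in item 3 could be read as McNemar on year-one and year-two pairs within each graft. For single-level patients that would answer objective 3. This stands as a possibility, but the plan does not state that contrast, the 15% between-graft hypothesis does not fit it, and the relative score rules it out for multilevel patients. A reader might infer that the plan has no two-year method at all. That is too strong: item 3 does give one for MagnetOs against autograft.

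The denominator is also partly settled. Re-using the primary method brings in its exclusions for revision and for non-evaluable levels, section 7.8 extends the revision exclusion to performance-related secondary outcomes, and section 2.3 implies that fully fused patients remain fused. A reader might infer that the plan intends to set a rescanned-only rate against the all-patient 50%. No passage says so; the plan simply does not exclude it.

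It is also tempting to call the carry-forward bias small, or smaller than the distortion from leaving patients out. The figures do not support this. A 5-point deficit is distorted by 2.7 points, while the false rise is 2.4 to 6.4 points, and the two are different quantities. The reading-error model ignores the panel procedure in Appendix C (two observers, a third on disagreement), so it indicates direction and rough size only.

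**Conclusion.** The point holds for two gaps in section 9.3 item 3. First, the assigned method does not estimate the one- to two-year change per graft, and the multilevel score can move against a graft that gained levels. This follows from the text alone. Second, no analysis section states how patients who are not rescanned enter the two-year figures.

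The sizes for the second gap (35% not rescanned, 23% one-year rate among the rescanned, factor 1.54) are exact for single-level patients under the plan's 50% and 70%. The effect appears weaker with more levels, but those figures rest on an assumed model. The c values and the 5–15% reading error are also assumptions.

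A reader might infer that the trial's main conclusion is at risk. It is not: one secondary objective is affected, and the primary analysis and sample size are untouched. The change should be made before two-year data are analysed.

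**What to change.** Reword section 9.3 item 3 as follows.

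1. **MagnetOs versus autograft at two years:** keep the primary method.
2. **Change over time:** use absolute level-by-side fusion in the existing GEE with treatment, time and time-by-treatment terms, clustered on patient. Do not use the relative side-versus-side score for change.
3. **Analysis set for both comparisons:** patients in the one-year analysis set, excluding those revised in year two (sections 7.8 and 9.1) and levels not evaluable at two years (section 9.1, Appendix C). Report the numbers excluded.
4. **Two-year status:** carry forward as fused only patients read as fully fused at one year and so not due a scan. Use the two-year reading for rescanned patients, so that losses count. Treat missed scans as missing. Do not set a rescanned-only two-year rate against the all-patient one-year rate.
5. **Reporting:** state the carry-forward assumption with the result, including that late loss of fusion in patients not rescanned is unobserved and that reading error biases the change upward.

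Best- and worst-case bounds for missed scans and a sensitivity analysis for reading error would be useful but are optional.

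The cost is SAP wording and a little more analysis. No extra scans or readers are needed. The upward bias and the unobserved late losses remain, but are disclosed.

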Although iliac crest donor site morbidity is often reported by patients, the relevance of donor site pain is disputable when the bone is harvested via the same incision as used for the spinal fusion.³ The preliminary results of the AxA study indeed indicate that there is no relation between the real donor site and the iliac crest that is indicated by blinded patients. To determine if the often reported high incidence of donor site pain can be explained by the knowledge of the patient where the bone graft was taken, we will not blind the patients for the donor site in this study. The outcomes measures reported by patients unblinded to the iliac crest donor site will be compared to the outcomes of the blinded patients from the AxA study.

5. Combine the study populations of the current study and the AxA study

To combine the study data of both the current study and the AxA study will allow investigations on more infrequent phenomena on a relatively large population. Such a phenomenon is for example adjacent segment disease. This is a longterm complication where the adjacent joints and intervertebral disc may wear faster and cause degenerative disease. The occurrence of adjacent segment disease may be related to length of the construct and restoration of the sagittal balance. The occurrence of typical complications like infection and pseudoarthrosis can be related to risk factors like comorbidities, smoking, length of instrumented segment and so on.

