7.3.1 Baseline data

After enrollment (see Chapter 10 for the recruitment and consent procedure), a preoperative baseline evaluation will be performed and the following data will be collected (CRF A):

- Month and year of birth
- Gender
- Smoking
- Pre-operative diagnosis
- Prior treatment to affected spinal levels
- Concurrent medical conditions
- ASA classification
- Disease related medication use (including NSAID use)
- Questionnaires
 - EQ-5D-5L
 - ODI
- VAS pain score
 - Back pain related to diagnosis
 - Leg pain related to diagnosis
 - Pain in left iliac crest
 - Pain in right iliac crest
 - Pain drawing

The EQ-5D-5L is a standardized instrument for use as a measure of health outcome. Applicable to a wide range of health conditions and treatments, it provides a simple descriptive profile and a single index value for health status that can be used in the clinical and economic evaluation of health care as well as population health surveys. The Oswestry Low Back Pain Disability Index (ODI) is an evaluation questionnaire related to patient perception of the effect of his/her current low back pain on activities of daily living. A Visual Analogue Scale (VAS) will be used to record back pain, leg pain and iliac crest pain at the left and right side at all evaluation points. As a supplement, patients will be asked to make a pain drawing to get a graphic representation of the pain and its physical distribution.

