7.3.2 Surgical and postoperative procedures

Patients will be operated according to standard surgical procedures for instrumented posterolateral fusions between T10 and S2, with the only exception that one side of the spine will be grafted with the synthetic ceramic material MagnetOs™ Granules instead of bone harvested from the iliac crest. A recommended surgical technique is provided in Appendix B. In advance, the participating orthopaedic surgeons of each center will receive instructions on appropriate use of MagnetOs™ Granules from the principal investigator. Any questions that may arise concerning the surgical aspects of using MagnetOs™ Granules or autograft will be answered by the principal investigator.

Standard prophylactic antibiotics will be given for at least 24 hours, according the local surgical guidelines of each center. A thrombosis prophylaxis will be used according to the surgeons' preference. If preferred by the surgeon, patients will receive a restraining brace or orthosis postoperatively in order to protect the spine from (excessive) movements. Mobilization will be encouraged on the first postoperative day; physiotherapy will be offered during hospitalization and ambulatory if indicated.

According to standard care, standing anteroposterior and lateral radiographs will be taken postoperatively during hospitalization.

During surgery and hospital admission, the following information will be collected (CRF B):

- Date of surgery
- Surgeon's name
- Surgical technique
 - Instrumented spinal levels
 - Levels of decompression
 - Performance of vertebral osteotomy
 - Use of interbody device
 - Insertion side of TLIF
 - Additional surgical procedures
- With the use of a 20ml syringe an estimation of the volumes (in mL) of:
 - 1) obtained local bone and 2) obtained iliac crest bone and 3) the ratio of local bone / iliac crest bone used for posterolateral fusion
 - Local bone (or mixed autograft) applied per level for interbody fusion
 - (Mixed) autograft used per posterolateral fusion level

- Estimation of volume of MagnetOsTM Granules per posterolateral fusion level (in cc)
- Iliac crest side used for bone harvesting (right/left)
- Iliac bone harvested via same incision (yes/no)
- Additional time required for bone graft harvesting (minutes)
- Allocation of MagnetOsTM Granules (left/right)
- Surgical time (skin to skin and total anaesthesia time (begin and end of sedation)
- Estimated blood loss (cc)
- Use of vancomycine powder

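### Section 9.3 item 4 tests the effect of blinding on donor-site pain by comparing pain scores across two non-randomised cohorts, with no side contrast or baseline adjustment, so a cohort difference in general pain could be read as a blinding effect

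*Combined protocol and SAP*

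**What the plan says.** Section 2.3 (rationale, item 4) sets up the question. Preliminary AxA results are said to show that "there is no relation between the real donor site and the iliac crest that is indicated by blinded patients". To learn whether knowledge of the harvest location explains the high reported incidence of donor-site pain, the protocol states that "we will not blind the patients for the donor site in this study".

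Section 9.3 item 4 has two parts. First: "VAS pain scores will be analyzed using the paired t-test, or Wilcoxon signed rank test in case of not-normally distributed data". What is paired with what is not stated. Then, for the blinding question: "pain scores reported by the patients of this study and the AxA study will be compared using the unpaired t-test or Mann-Whitney U test". No side contrast, change from baseline, covariate or visit is named.

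The data for a side contrast exist in this study. Section 7.3.1 has the VAS "will be used to record back pain, leg pain and iliac crest pain at the left and right side at all evaluation points". Section 7.3.3 repeats both crest scores at 6 weeks, 3 months, 1 year and 2 years, and section 7.3.2 records which crest was harvested.

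AxA is a separate trial with surgery between October 2013 and July 2016 (section 1). Section 2.3 item 1 defends unpaired comparison across the trials on the ground of identical design and eligibility, but that text is written for the comparison with AttraX Putty.

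Section 7.2 bears on the same objective: it says that the harvest side is not disclosed to the patient.

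**The concern.** The hypothesis in section 2.3 is about location: does knowing where the graft was taken raise the pain reported there? A VAS for one iliac crest after lumbar surgery, often with harvest through the same incision, can also carry general low-back and pelvic pain. The two cohorts were enrolled in different years and were not randomised against each other, so that general level may differ for reasons unrelated to blinding.

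If the unpaired test is run on donor-side scores as they stand, such a difference enters in full. It can produce an apparent blinding effect or mask a real one. The unharvested crest of the same patient carries the shared part of the pain and is already scored, yet the between-study comparison makes no stated use of it. At stake is the interpretation of secondary objective 4.

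**Working it through.** **Inputs from the documents.** Enrolment is 100, with about 15% assumed not evaluable at one year (section 4.4): 100 × (1 − 0.15) = 85. AxA had 100 patients operated according to its protocol (section 1). The documents give no SD, VAS range, sample size or effect size for the pain comparison, so there is no figure of the plan to reproduce. The 84-patient calculation in section 4.4 and Appendix A concerns fusion and does not bear on this point.

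**Assumptions.** VAS 0-10 with SD 2.5; 85 per trial (the 15% is borrowed from CT evaluability); two-sided 5% test; no true blinding effect; a cohort shift d in general pain that adds equally to both crests.

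**Step 1: what each comparison estimates.** The between-study difference in donor-side score is d. The difference in harvested-minus-unharvested score is d − d = 0.

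**Step 2: false significance on donor-side scores.** SE = 2.5 × √(2/85) = 0.383. The rejection probability is Φ(−1.96 + d/SE) + Φ(−1.96 − d/SE).

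| Shift d (points) | d/SE | Donor-side score | Contrast |
|---|---|---|---|
| 0.3 | 0.78 | 12% | 5% |
| 0.5 | 1.30 | 26% | 5% |
| 0.8 | 2.09 | 55% | 5% |

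**Step 3: sensitivity to sample size.** With 85 to 100 per trial, the rates are 10-11% for a shift of 0.1 SD, 26-29% for 0.2 SD and 50-56% for 0.3 SD. Simulation at 0.3 SD with a left-right correlation of 0.7 gave 50% and 56% for the t-test, 47% and 56% for the Mann-Whitney test, and about 5% for the contrast.

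**Step 4: precision of the contrast.** SE = 2.5 × √(2(1 − r)) × √(2/85), where r is the correlation between the two crests. The factor √(2(1 − r)) is 1.18, 1.00, 0.77 and 0.63 for r = 0.3, 0.5, 0.7 and 0.8. The SE is therefore 0.454, 0.383, 0.297 and 0.243. The contrast is less precise than the donor-side score only when r is below 0.5.

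**Step 5: is there a difference in blinding to estimate?** Section 2.3 has AxA patients blinded to the donor site and patients in this study unblinded. Section 7.2 withholds the harvest side from patients in this study. If section 7.2 governs, the intended difference in blinding between the trials may not exist, and no choice of outcome variable repairs that.

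**The case against.** **The plan does not say raw scores.** This stands. A reader might infer that the sponsor chose unadjusted donor-side scores, or that the objective as written cannot separate blinding from cohort effects. The text supports neither: an unpaired test can be applied to donor-side scores, changes from baseline or side differences, and none is excluded. What the documents do show is that the variable is undefined and that no contrast or baseline adjustment is specified.

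**The paired test may already supply the contrast.** It might, if it pairs the two crests; it could equally pair visits. Even on the favourable reading it is not linked to the between-study comparison that section 9.3 assigns to the blinding question.

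**The contrast is a different quantity.** This also stands. Section 2.3 speaks of the reported incidence of donor-site pain. If knowing about the harvest changes reporting on both crests, that part cancels in the contrast. It would therefore be wrong to reduce the donor-side comparison to description only.

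**The cohorts should be alike, since design and eligibility match.** That is some reassurance, but equal criteria do not guarantee equal pain levels. Nor does the contrast remove all confounding, as a reader might suppose: side-specific differences such as harvest technique or centre mix remain.

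**The AxA data are unseen.** The documents imply, but do not state, that AxA recorded a VAS for each crest.

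**Conclusion.** The point holds in a limited form. Section 9.3 item 4 leaves the pain variable open and specifies neither a side contrast nor a baseline adjustment for a comparison between non-randomised cohorts. If donor-side scores are used as they stand, a shift of 0.3 to 0.8 points in general pain produces false significance in about 12% to 55% of cases, against 5% for the contrast. These rates are illustrations, not predictions for this trial: the SD, the shifts and the equal contribution of general pain to both crests are all assumed. The contrast captures only the side-specific part of any blinding effect.

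The conflict between sections 2.3 and 7.2 comes first, because objective 4 presupposes a difference in blinding. This is an unpowered secondary objective, so the change is worth making but does not touch the primary efficacy or safety conclusions.

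**What to change.** In section 9.3 item 4:

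1. Define the main between-study outcome, per patient and visit, as VAS of the harvested crest minus VAS of the unharvested crest. Use the recorded harvest side and adjust for the same contrast at baseline.
2. Keep the between-study comparison of donor-side scores alongside it, since a blinding effect on both crests cancels in the contrast.
3. State what the paired test pairs and which visit the comparison refers to.
4. State that the result is a non-randomised association in which side-specific cohort differences remain.
5. Confirm that AxA recorded VAS for both crests, at baseline as well. If it did not, the baseline-adjusted contrast cannot be compared between the trials.
6. Reconcile sections 2.3 and 7.2 on whether patients know the harvest side.

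For this study items 1 to 4 cost only wording, because both crest scores, the baseline scores and the harvest side are already collected. The downsides are lower precision if the crests correlate below 0.5, and an outcome limited to the side-specific part of the effect.
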